Sphenopalatine Ganglion Block for PostDural Puncture Headache in Obstetric Postpartum Patients

Protocol: 16-1596

NCT: 02962427

Date: 10/26/2016

Protocol Synopsis Sheet

Below is the format to follow for the concept sheet for protocols. The point of a synopsis is that the critical elements of the protocol are summarized in a succinct manner. Bulleted or numbered lists should be used wherever possible.

Please limit your protocol concept sheet synopsis to four-to-five (4 - 5) pages (using 11-point Arial or 12-point Times New Roman typeface with one-inch margins). Please include your biosketch in the NIH format.

SYNOPSIS

Title of Study: Sphenopalatine Ganglion Block for PostDural Puncture Headache in Obstetric Postpartum Patients
Sponsor: None
Investigators: [name] MD MS, [name] MD, [name] MD PhD
Research Mentor: None
Study Center(s): University of Colorado Hospital
Clinical Phase (I, II, III)
Hypothesis: Sphenopalatine Ganglion Block is as effective as epidural blood patch for relieving post-dural puncture headache pain in postpartum obstetric patients
Aims: Specific Primary Aim: Compare the effectiveness of a sphenopalatine ganglion block to an epidural blood patch for postdural puncture headache relief in randomized postpartum parturients over a 48 period. Specific Secondary Aim: Compare the effectiveness of a sphenopalatine ganglion block in known versus unknown dural puncture for postdural puncture headache relief in randomized postpartum parturients over a 48 period.
Primary Objective(s): Compare pain scores after sphenopalatine ganglion block or epidural blood patch for postdural puncture headache treatment in postpartum parturients.
Secondary Objective(s): Evaluate effectiveness of sphenopalatine ganglion block and epidural blood patch for known and unknown dural puncture in postpartum parturients with PDPH.
Exploratory Objective (s): To determine if a minimally invasive technique (sphenopalatine ganglion block) is as effective in treating post-dural puncture headache in postpartum parturients as an invasive technique (epidural blood patch)

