Study Design/Methods: After approval by the Institutional Review Board and completion of informed patient consent, we will include obstetric postpartum parturients presenting with a diagnosis of post-dural puncture headache (PDPH) as defined by the International Classification of Headache Disorders. These are both procedures utilized for the treatment of post-dural puncture headaches on the labor and delivery floor currently. Each study participant will be randomized to receive either an EBP or a SPGB; however, if the SPGB or EBP fails initially or subsequent failure within the 48 hour time period, the participant will be offered another SPGB or an EBP if in the SPGB arm or simply another EBP if in the EBP arm.

Maximum of 2 SPGB or EBP per patient.
 
We will also collect patient age, gravity, parity, BMI, ASA status, history of any headaches including migraines during or prior to pregnancy, details and timing of the original neuraxial procedure, delivery mode and details and other interventions attempted to relieve the headache (including repeated SPGB or EBP within 48 hours). We will document resolution of headache at 1 hour, 24 hours and 48 hours after procedure utilizing NRS scores (1-10). All documentation will be stored and accessed in our electronic medical record (Epic®).

Study Period: 7/1/2016 – 7/1/2019

Study Population: Postpartum obstetric parturients diagnosed with a post-dural puncture headache.

Number of Patients: 100 patients over a three year period

Timeline:
 
5/1/2016: Submission of IRB protocol
 
7/1/2016: IRB approval and beginning of enrollment of study subjects
 
7/1/2019: Completion of study
 
7/1/2019-9/1/2019: Completion of publication for submission

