Audits will consist of a review of the regulatory documents, consent forms, and source data verification. Results and recommendations from audits will then need to be submitted by the PI to the IRB of record at the time of the continuing review.

Risks to Patients: These are both procedures utilized for the treatment of post-dural puncture headaches on the labor and delivery floor currently.

Epidural blood patch: Common side effects include tenderness at site of injection and pressure in the lumbar spine. Rare risks include bleeding, infection, nerve damage, paralysis, dural puncture, no relief of symptoms.

Sphenopalatine ganglion block: Common risk is failure to relieve symptoms. Rare risks are damage to intranasal tissue or structures, anosmia or allergic reaction to medication.

Statistical Methods: There is a paucity of data in the literature evaluating the effect of EBP and SNB on PDPH pain using a numerical rating scale (NRS) or a visual analog scale (VAS). Most studies report outcomes in terms of complete, partial, or no relief. One study in 108 emergency department patients found that the correlation between a 10-point NRS scale and a VAS was 0.94 (95% CI 0.93-0.95), indicating that a verbally administered NRS can be substituted for the VAS in acute pain management. From our review of the few studies reporting NRS or VAS data, the baseline NRS or VAS in patients with PDPH is about 8-9 with a standard deviation of ± 1.5 , which might be reduced to about $3-4 \pm 3$ 1-6 hours after treatment, and perhaps to $1-2 \pm 1.5$ 24-48 hours after treatment. Assuming that we wish to detect a 1-2 unit difference in the NRS between the 2 treatment groups as being clinically meaningful, we calculate that we will need to randomize about $n = 100$ patients (50 patients in each treatment group) to achieve a statistical power of 90% for the trial.

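### The primary pain scale is written as NRS 1-10, with no zero for a resolved headache, and this conflicts with the plan's own 24-48 h planning values

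*Combined protocol and SAP*

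**What the plan says.** The range of the outcome scale appears once, in the Synopsis under Study Design/Methods: "We will document resolution of headache at 1 hour, 24 hours and 48 hours after procedure utilizing NRS scores (1-10". Statistical Methods cites a study in which "the correlation between a 10-point NRS scale and a VAS was 0.94 (95% CI 0.93-0.95", but this does not supply anchors either.

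The score is the primary outcome. The primary objective is: "Compare pain scores after sphenopalatine ganglion block or epidural blood patch for postdural puncture headache treatment in postpartum parturients". The analysis compares NRS means between arms at baseline and at 1, 24 and 48 hours with a longitudinal mixed linear model.

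The planning values in Statistical Methods come from published NRS or VAS data:

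- at baseline, the score "is about 8-9 with a standard deviation of ± 1.5";
- early after treatment, it might be "reduced to about $3-4 \pm 3$ 1-6 hours after treatment";
- later, "perhaps to $1-2 \pm 1.5$ 24-48 hours after treatment".

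The target is set by: "Assuming that we wish to detect a 1-2 unit difference in the NRS between the 2 treatment groups as being clinically meaningful". With 50 patients per group, 90% power is claimed for the trial as a whole. Alpha, sidedness and the time point to which the 90% refers are not stated.

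**The concern.** The plan uses the scale to document that a headache has gone, yet its lowest value is 1. Read literally, patients with no pain and patients with minimal pain share a score, or staff improvise with 1, 0 or a blank. Complete relief, which Statistical Methods itself names among the usual ways of reporting outcome in this field, could then not be separated from slight pain. It could not be recovered after data collection.

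The floor would not cancel between arms. Recording every 0 as 1 raises each arm's mean by that arm's proportion of pain-free patients. The arm doing better has more of them, so its mean rises more and the difference narrows. The effect is largest where most patients are pain-free, which on the plan's figures is 24-48 hours. The stated hypothesis is that the block is as effective as the blood patch, so a measurement that narrows real differences would err in the direction of that hypothesis.

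**Working it through.** **1. The plan's own figure.** Inputs from Statistical Methods: 50 per arm, and a 1-unit difference with the 24-48 h SD of 1.5. Two-sided alpha of 0.05 and no dropout are assumed.

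Power = Φ(δ / (SD × √(2/n)) − 1.96) = Φ(1 / (1.5 × 0.2) − 1.96) = Φ(1.37) = 91.5%, or 91.0% with the t distribution. For 90% power, n per arm = 2 × (1.96 + 1.2816)² × 1.5² / 1² = 47.3, so 48 (49 with the t distribution).

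The stated 100 patients and 90% are therefore reproduced. A 2-unit difference with the early SD of 3 has the same ratio, 0.667, and reproduces them equally well.

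**2. Do the planning values fit a 1-10 scale?** The largest possible SD at mean m is √((m − 1)(10 − m)).

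- m = 1: √(0 × 9) = 0.
- m = 1.25: √(0.25 × 8.75) = 1.48.
- m = 2: √(1 × 8) = 2.83.
- m = 3: √(2 × 7) = 3.74.

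An SD of 1.5 is impossible until the mean is just above 1.25. The low end of the 24-48 h range therefore contradicts the scale. The upper end, the early values and the baseline values do not. This step needs no assumption about the distribution of scores.

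**3. What happens if 0 is recorded as 1?** The documents give no score distribution, so three were fitted on 0-10 to the stated means and SDs: beta-binomial, maximum-entropy and censored normal. Every 0 was then set to 1.

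Example (beta-binomial, means 1 v 2, SD 1.5): 55% and 16% of patients score 0. The means become 1.55 and 2.16, and the difference is 1.00 − (0.55 − 0.16) = 0.61. The SD falls to 1.25. Power = Φ(0.61 / (1.25 × 0.2) − 1.96), which is about 69% (68% with the t distribution).

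Ranges below cover the three distributions and both the normal and t formulas, at 50 per arm:

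| True means, SD | Scoring 0, better v worse arm | Difference with floor | SD with floor | Power on 0-10 | Power with floor |
|---|---|---|---|---|---|
| 1 v 2, 1.5 | 52-58% v 16-20% | 0.61-0.66 | 1.22-1.25 | 91% | 68-75% |
| 1.5 v 2.5, 1.5 | 31-35% v 8-10% | 0.75-0.77 | 1.28-1.32 | 91% | 82-84% |
| 2 v 3, 1.5 | 16-20% v 3-5% | 0.85-0.87 | 1.35-1.38 | 91% | 88-89% |
| 1 v 3, 1.5 | 52-58% v 3-5% | 1.47-1.52 | 1.29-1.32 | over 99% | over 99% |
| 2.5 v 4.5, 3 | 35-44% v 10-13% | 1.69-1.75 | 2.74-2.80 | 91% | 86-88% |
| 3 v 5, 3 | 26-33% v 7-9% | 1.77-1.82 | 2.78-2.83 | 91% | 88-90% |

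Simulated t-tests (20,000 per case) came out up to about 2 points lower with the floor. The 1 v 2 case gave 68-74%, against 89-90% on 0-10.

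The SD shrinks along with the difference. Holding it at 1.5 in the 1 v 2 case would give 53-59% and overstate the loss.

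**4. If 1 means no pain.** If every score is simply moved up by a constant, the differences and SDs are unchanged and no power is lost.

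**The case against.** A reader might infer that the stated 90% power is not delivered at 24-48 h. The documents do not support that, for four reasons.

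- The 90% is claimed for the trial and not for any time point. The 2-unit, SD 3 pairing explains it as well as the 1-unit, SD 1.5 pairing, and loses only a few points.
- The loss requires pain-free patients to be scored 1 together with those in minimal pain. No section says so. A form with 1 anchored as no pain would record resolution and cost no power.
- The misfit in the planning values can itself be read as a sign that the authors had 0-10 in mind and wrote the range loosely. The values are also hedged and drawn from mixed NRS and VAS reports.
- The calculations are two-group comparisons at one time point. The planned mixed model's power also depends on within-patient correlation, which is not given.

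All four stand, and they limit what can be said about power. It also stands that 1 v 2 is the least favourable case in the table. It is not contrived, however: those means are the two ends of the plan's 24-48 h range, and their gap is the lower end of its target difference.

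A reader might also infer that the scale biases the trial towards its hypothesis. That too is conditional on the scoring. The larger mismatch, an as-effective-as hypothesis with no margin and a sample size set to detect a difference, would exist on any scale.

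None of this removes the contradiction in the text. If 1 was meant as no pain, a mean of 1 with SD 1.5 is still impossible. If 0-10 was meant, the written range is wrong.

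**Conclusion.** The point holds as a defect in the written outcome scale. The only stated range has no zero, its anchors are undefined, and it is incompatible with the low end of the plan's own 24-48 h assumptions. That conclusion rests on the text and on simple arithmetic.

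The effect on power is conditional. If zeros are recorded as 1, power for a 1-unit difference at SD 1.5 would be about 68-75%, 82-84% or 88-89% instead of 91%, depending on whether the means are 1 v 2, 1.5 v 2.5 or 2 v 3. For a 2-unit difference it would remain over 99% at 1 v 3, and be about 86-90% at SD 3. These figures assume two-sided 0.05, no dropout, a single time point and fitted score distributions. The loss is nil if 1 is anchored as no pain or if 0-10 was intended. A flat statement that the trial falls short of its 90% is not warranted. The scale should be corrected because the correction is simple and pain-free scores merged with minimal pain cannot be separated later.

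**What to change.** In Study Design/Methods, replace the 1-10 range with NRS 0-10, where 0 = no headache and 10 = worst imaginable, and apply it at baseline, 1, 24 and 48 hours. Use the same range and anchors in the REDCap form and in the medical-record entry from which it is filled. State that a score of 0 is reported as complete resolution.

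The cost is one wording change and one form edit, with no added patients, visits or procedures. The planning values can stay as they are, since a mean of 1 with SD 1.5 is possible once the scale includes 0. If any scores were collected before the change, the report should say how pain-free patients were scored.

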The study data will be entered into REDCAP. Frequency distributions will be calculated for all variables to determine if the distributions of values look reasonable and if there are any outliers in the data. Suspected outliers will be corrected if needed, or truncated, or recoded as missing. Distributions will be tested for a normal (Gaussian) distribution. The primary statistical analysis will be by intention-to-treat. Treatment groups will be compared on demographic and clinical characteristics at baseline (Table 1). A CONSORT diagram will be prepared to describe screening and entry of patients into the clinical trial, and disposition of all patients after randomization. NRS means and standard deviations will be calculated for each treatment group at baseline, and 1, 24, and 48 hours after treatment. These mean values between the 2 treatment groups over time will be tested for statistical significance using a longitudinal mixed linear model. Side effects, adverse effects, and serious adverse effects will be recorded and compared for

each treatment group. Publication of results will follow the CONSORT 2010 checklist.

Funding/Budget: Funding for the statistical analysis will be requested from the Department of Anesthesiology. All treatments and supplies are currently employed on the labor and delivery deck, no additional funding is needed.

Requested Departmental Support: Funding for the statistical analysis will be requested from the Department of Anesthesiology. All treatments and supplies are currently employed on the labor and delivery deck, no additional funding is needed.

Expected Outcomes: After completion of this study, we will be able to determine the effectiveness of SPGB for the treatment of PDPH when compared to EBP placement. If SPGB are effective, this could change the management and algorithm in the treatment of PDPH for postpartum parturients.

Please include your biosketch in the NIH format (follow link below)

<http://www.google.com/url?sa=t&rct=j&q=&esrc=s&source=web&cd=3&ved=0CDoQFjAC&url=http%3A%2F%2Fgrants.nih.gov%2Fgrants%2Ffunding%2Fphs398%2Fbiosketchsample.doc&ei=wMbxUo-hD8b4yAHd-4GADw&usq=AFQjCNE4b9iv7E-afLxtF7fDYQvH9U-Pcg&bvm=bv.60799247,d.aWc&cad=rja>

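### The outlier rule lets valid 24 and 48 h pain scores be truncated or deleted on suspicion, and those scores may be the treatment failures

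*Combined protocol and SAP*

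**What the plan says.** Under Statistical Methods, the data-cleaning step covers the whole data set: "Frequency distributions will be calculated for all variables to determine if the distributions of values look reasonable", and whether outliers are present. The action follows: "Suspected outliers will be corrected if needed, or truncated, or recoded as missing". Nothing exempts the NRS, defines an outlier, limits truncation or deletion to proven errors, masks the person deciding, or calls for an analysis of the uncleaned data.

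The same section states: "The primary statistical analysis will be by intention-to-treat". The NRS means at baseline, 1, 24 and 48 h are then compared with a longitudinal mixed linear model.

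On expected values, the section says that "the baseline NRS or VAS in patients with PDPH is about 8-9" (SD 1.5). It expects 3-4 (SD 3) at 1-6 h and 1-2 (SD 1.5) at 24-48 h. Study Design/Methods gives the scale as 1-10.

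Risks to Patients says of SPGB: "Common risk is failure to relieve symptoms". For EBP, the same outcome appears among the rare risks: "Rare risks include bleeding, infection, nerve damage, paralysis, dural puncture, no relief of symptoms".

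**The concern.** The sentence may be meant for keying errors, but it does not say so. Truncation and recoding to missing are offered as options in their own right, triggered by suspicion. At 24 and 48 h most patients are expected to be near the bottom of the scale, so the score that looks most out of place is that of a patient whose headache has not resolved. That is the event the trial is meant to measure.

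The effect need not be equal in the two arms. If non-relief is common after SPGB and rare after EBP, as the risk lists say, the scores at risk sit mainly in the SPGB arm. Shrinking or deleting them pulls the difference toward zero, in the direction of the stated hypothesis. Discarding valid outcomes of randomised patients because they are high also undercuts the stated intention-to-treat analysis. The mixed model does not repair this, because the scores would be missing on account of their own value.

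**Working it through.** **The plan's sample size.** Alpha is not stated; two-sided 0.05 is assumed. For a difference of 1 unit with SD 1.5, n per arm = 2 × (1.96 + 1.282)² × (1.5/1)² = 47.3, so 48 per arm (49 by the t-test). Power at 50 per arm is about 91%. The plan's 100 patients at 90% power is reproduced, so the sample size is not at fault. A difference of 2 with SD 3 gives the same result.

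**How far out is an unrelieved score?** z = (score − mean) / SD, with the plan's figures:

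- 24-48 h: (8 − 2)/1.5 = 4.0 to (9 − 1)/1.5 = 5.3.
- 1-6 h: (8 − 4)/3 = 1.3 to (9 − 3)/3 = 2.0.

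A mean + 2 SD limit at 24-48 h falls at 1 + 3 = 4.0 to 2 + 3 = 5.0. A mean + 3 SD limit falls at 1 + 4.5 = 5.5 to 2 + 4.5 = 6.5. All of these lie inside the 1-10 scale and below baseline pain. The exposure is therefore at 24 and 48 h, and much less at 1 h.

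**Size at one late time point.** The plan gives no cut-off and no failure rates, so the following are assumptions: 50 per arm; successes about 1.2 (SD 1.2); failures about 8.5 (SD 1.5); scores rounded and clipped to 1-10. A failure means a patient still in pain at that time point, after any repeat procedure. Limits come from the pooled observed scores: Tukey fence = Q3 + 1.5 × IQR, or mean + 3 SD. The table gives mean differences in NRS units over 20,000 simulated trials per row.

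| Failures (SPGB v EBP) | All scores | Tukey, missing | Tukey, truncated | 3 SD, missing | 3 SD, truncated |
|---|---|---|---|---|---|
| 5% v 1% | 0.28 | 0.00 | 0.08 | 0.02 | 0.20 |
| 10% v 2% | 0.55 | 0.00 | 0.17 | 0.16 | 0.47 |
| 15% v 5% | 0.68 | 0.01 | 0.27 | 0.44 | 0.65 |
| 20% v 5% | 1.02 | 0.04 | 0.48 | 0.83 | 1.00 |
| 30% v 10% | 1.36 | 0.34 | 0.96 | 1.35 | 1.36 |
| 40% v 20% | 1.36 | 1.26 | 1.33 | 1.36 | 1.36 |

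The harm is largest when failures are few. When they are frequent they widen the observed spread and are no longer flagged. On a 0-10 scale the 20% v 5% row is 1.06, then 0.07 / 0.60 / 0.91 / 1.04.

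**Consistency check.** Under these assumptions an overall SD of 1.5 corresponds to only about 3% failures (SD 1.43 at 3%, 1.70 at 5%). The mean + 3 SD limit is then near 6 and a score of 8-9 is flagged. At 12.5% pooled failures (20% v 5%) the SD is 2.4 and the limit about 9.7, so only a 10 is flagged.

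**A different assumed mixture.** With failures scoring 4-8, successes 0-3, failure rates 25.5% v 5% and fixed limits from the plan's own figures (4.0-6.5), a difference of 1.02 becomes 0.16-0.55 if recoded to missing and 0.61-0.93 if truncated. A limit at that mixture's own pooled mean + 3 SD (8.0) removes nothing.

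**Mixed model.** This used a random intercept, treatment by time, 250 trials and baseline 8.5 (SD 1.5). At 1 h, successes were 2.8 (SD 2.5) and failures 8.0 (SD 1.5); failure status was the same at 24 and 48 h. At 20% v 5% the 48 h difference goes from 0.94 to 0.04 / 0.41 / 0.78 / 0.92, in the table's column order. The 1 h difference hardly moves (0.72 to 0.68 at worst).

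**The case against.** The strongest reply is that this is ordinary data checking. The sentence follows data entry into REDCap, an 8 or 9 is plainly a possible score, and nothing says such a score would be treated as an outlier. That is a fair account of the likely intent, and the documents do not show that valid scores would be removed. But the wording permits it. Source data verification at audit and the data and safety monitoring committee's duty for data quality are not tied to this rule, and a source check does not stop an analyst truncating a correctly recorded 9.

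Several points about size stand:

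- The 4.0-5.3 SD figure rests on an SD of 1.5, which fits few failures. In that range the difference available to lose is small (0.28 units at 5% v 1%, against the plan's 1-2 unit target).
- At 20% v 5%, near-total loss needs a Tukey fence with deletion, which removes about 10 of 50 scores in one arm and 3 of 50 in the other. The plan names no such fence, but it names no other limit either.
- Truncation also reduces variance, so power falls less than the mean difference. At 20% v 5%, with a two-sided 0.05 t-test, power is about 58% with all scores, 58% with 3 SD truncation, 47% with 3 SD deletion, 43% with Tukey truncation and 5% with Tukey deletion.
- Direction depends on unequal failure. With 10% failures in both arms no option biases the difference. Repeat procedures within 48 h, including EBP after a failed SPGB, could narrow any imbalance; they are not modelled separately.

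On intention-to-treat, allocation is indeed unchanged, truncated scores stay in, and a patient with one deleted score still contributes other visits. The damage is selective loss of outcomes. That still defeats the purpose of the principle.

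**Conclusion.** The concern holds and should be fixed. As written, the rule allows genuine unrelieved-pain scores at 24 and 48 h to be shrunk or deleted without evidence of error and without masking.

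That the text permits this is certain. The size is not: it runs from almost none to almost all of the treatment difference, and it turns on a cut-off, a choice between truncation and deletion, and failure rates that the plan does not give. At the assumed 20% v 5%, a difference at the plan's 1-unit threshold can disappear or survive nearly intact according to a choice left open until the data are seen. A bias toward no difference follows only if failures are commoner after SPGB, which the plan's risk lists suggest but do not quantify.

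**What to change.** Replace the outlier sentence with: *Values outside the permitted range or suspected to be entry errors are checked against the source record (Epic), with treatment allocation masked, and corrected only if the source differs. An out-of-range value that cannot be resolved from source is set to missing. Every in-range NRS score not contradicted by source is kept unchanged in the primary analysis, and all changes are logged.*

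The cost is one sentence and a little checking against records that the plan already keeps in Epic. The observed SD may be larger than with trimmed data.

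### The mixed model may treat baseline NRS as one of the tested outcomes, and no deciding contrast is named; making baseline a covariate and fixing one post-treatment contrast costs almost nothing

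*Combined protocol and SAP*

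**What the plan says.** The efficacy analysis is two sentences in Statistical Methods. The first is descriptive: "NRS means and standard deviations will be calculated for each treatment group at baseline, and 1, 24, and 48 hours after treatment". The second is the test: "These mean values between the 2 treatment groups over time will be tested for statistical significance using a longitudinal mixed linear model". Model terms, covariance structure, the coding of time, the deciding contrast and the role of baseline are not given.

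The rest of the synopsis does not fill the gap:

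- **Primary Objective(s)** compares pain scores after the two procedures and names no time.
- **Aims** gives only a window: "for postdural puncture headache relief in randomized postpartum parturients over a 48 period".
- **Study Design/Methods** records NRS at 1, 24 and 48 h with equal standing. After a failed first treatment within 48 h, "the participant will be offered another SPGB or an EBP if in the SPGB arm".
- **The sample-size text in Statistical Methods** reads "Assuming that we wish to detect a 1-2 unit difference in the NRS between the 2 treatment groups as being clinically meaningful" and attaches that difference to no time point.

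**The concern.** The phrase opening the second sentence refers back to means that include baseline. On that reading a score taken before treatment is one of the outcomes on which the arms are tested. Randomisation makes its expected difference zero, so it tells us nothing about the treatment effect as an outcome, though it is useful as a covariate.

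Two things are at stake. First, the result that decides the trial could be a group effect over all times, a group-by-time test, a post-treatment average or a difference at one time, and the choice could be made after the data are seen. Second, under the four-time group effect, a real post-treatment difference is averaged with a zero and so is understated.

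**Working it through.** **Inputs from Statistical Methods.** 50 per arm; SD 1.5 at baseline, 3 at 1-6 h (used for 1 h), 1.5 at 24-48 h; difference 1-2 units; power 90%.

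**Assumed, because the plan gives no figure.** Two-sided alpha 0.05; the same correlation r between any two times, with r = 0.1/0.2/0.3/0.5; complete data; normal approximation.

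**1. The plan's own figure.** Per arm, n = 2(1.960 + 1.282)² × (SD/difference)². With 1 unit and SD 1.5: 2 × 10.51 × 2.25 = 47.3, so 48 (49 by t-test). At 50 per arm SE = √(2 × 2.25/50) = 0.30, and power = Φ(1/0.30 − 1.96) = Φ(1.37) = 0.915 (0.91 by t-test). With 2 units and SD 3, SE = 0.60 and 2/0.60 is the same ratio, so the power is the same. The stated N therefore reproduces equally well at 1 h and at 24-48 h and identifies neither. One unit with SD 3 would have 38%.

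**2. Group effect averaged equally over four times; true effect 1 unit at 1, 24 and 48 h.** Estimate = (0 + 1 + 1 + 1)/4 = 0.75. The squared SDs sum to 15.75 and the six pairwise SD products to 20.25, so Var = (2/50) × (15.75 + 40.5r)/16. At r = 0.5 this is 0.04 × 36/16 = 0.09, SE = 0.30, and power = Φ(0.75/0.30 − 1.96) = Φ(0.54) = 0.705.

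**3. Mean of the three post-treatment times, same effect.** Estimate = 1. Unadjusted Var = (2/50) × (13.5 + 22.5r)/9. The covariance of baseline with the post-treatment mean is r × 1.5 × (3 + 1.5 + 1.5)/3 = 3r, so adjusting for baseline removes (3r)²/2.25 = 4r² from the bracketed term after division by 9. At r = 0.5: 0.04 × (2.75 − 1) = 0.07, SE = 0.265, power = Φ(3.78 − 1.96) = 0.966.

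**4. Group-by-time with categorical time, same effect.** This is a 3-df Wald test on the three changes from baseline. The noncentrality is 8.54/9.60/10.95/15.28.

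| Test, 1 unit at all post-treatment times | r = 0.1 | 0.2 | 0.3 | 0.5 |
|---|---|---|---|---|
| Four-time group effect (estimate 0.75) | 92% | 87% | 81% | 71% |
| Group-by-time, 3 df | 69% | 74% | 80% | 92% |
| Post-treatment mean, unadjusted | 97% | 94% | 92% | 85% |
| Post-treatment mean, baseline-adjusted | 97% | 96% | 95% | 97% |

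At low correlation nearly all of the gain comes from leaving baseline out of the average. At r = 0.5 it splits into about 15 points from that and 11 from adjustment.

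**5. Other effect patterns.** With 2 units at 1 h and 1 unit later, the four-time group effect has 99/98/97/92% and the 3-df test 88/91/94/99%. With 2 units throughout, both exceed 99%.

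**6. Room for choice.** If any of the three single-time tests could be called decisive, the chance under the null that at least one reaches p < 0.05 is 1 − 0.95³ = 0.143 if they are independent, and 0.11-0.14 by simulation at r = 0.3-0.7.

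**The case against.** The sentence that lists baseline is descriptive, and the model is never written out. The primary objective points to scores after treatment, and testing groups over time fits a group-by-time test at least as well as a group effect. In a group-by-time test, baseline as a response does not dilute the effect. All of this stands, so the claim is that baseline may be a tested outcome, not that it is.

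Four stronger readings are tempting, and the documents do not support them.

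- **That the trial is underpowered.** The loss depends on an unstated correlation and on the effect pattern. It is small with 2 units at 1 h and 1 unit later, and absent in practice with 2 units throughout. An additive model with unstructured covariance can be made to show 56% power and an estimate of 0.50 (r = 0.5; 2 units at 1 h, 1 unit later), but it gives the 1 h score a negative weight of about −0.12 and nothing in the plan proposes it.
- **That the plan is tilted towards its hypothesis that "Sphenopalatine Ganglion Block is as effective as epidural blood patch for relieving post-dural puncture headache pain".** Shrinkage towards zero arises only under the group-effect reading, and it favours that conclusion only if non-significance is taken as equivalence. That is the missing-margin problem, which is separate.
- **That group-by-time necessarily means 3 df.** This assumes categorical time; linear time would give 1 df.
- **That 24 h is the implied primary time.** The sample size fits 48 h and 1 h as well, and the aim covers the whole 48 h.

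**Conclusion.** The point holds as a free improvement, not as a flaw that invalidates the trial. Two parts need no assumption: the plan names no deciding contrast and no role for baseline, and its natural reading admits baseline as an outcome. That the sample size fits 1 h and 24-48 h equally well rests only on the plan's SDs and an assumed two-sided 0.05.

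The size of the gain is conditional. For a constant 1-unit effect, moving baseline from the average to a covariate restores the estimate from 0.75 to 1 and raises power by about 5 points at correlation 0.1 and about 26 at 0.5. Compared with the 3-df test, the adjusted mean gains about 28 points at 0.1 and about 4 at 0.5. If the true differences are larger, there is little or nothing to gain in power, and the benefit is a result fixed in advance.

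**What to change.** Before outcomes are compared by arm, amend Statistical Methods as follows.

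1. Model the 1, 24 and 48 h scores as outcomes, with baseline NRS as covariate (or with baseline means constrained equal between arms), treatment, categorical time and treatment-by-time. State the covariance structure.
2. Name one primary contrast with its 95% CI. The baseline-adjusted SPGB minus EBP difference averaged over 1, 24 and 48 h keeps the 48 h aim. A single adjusted time, 24 or 48 h, is an acceptable alternative. Report the per-time differences as secondary.
3. Restate the 1-2 unit difference and its SD for that contrast. For the averaged contrast, the workings above give an adjusted SD of √1.71/√1.84/√1.89/√1.75 = 1.31/1.36/1.37/1.32, and a CI half-width of 1.96 × SD × √(2/50) = 0.51/0.53/0.54/0.52 units.
4. State that under intention-to-treat the contrast compares strategies that include any repeat treatment or SPGB-to-EBP crossover, and that this may itself pull the difference towards zero.

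The cost is SAP wording, with no extra patients or visits. The pre-procedure NRS is not in the list of collected data in Study Design/Methods, although Statistical Methods relies on it, so the data form must carry it. This change does not supply a margin for the equal-effectiveness hypothesis.
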